#### 8.2.4 ELECTROCARDIOGRAMS

Participants will undergo telemetry beginning on Day -1 through 50 hours after the start of infusion ([Table 8](#)). Five-minute telemetry data extraction periods should begin after 10 minutes of rest in a semi-reclined position, and when applicable, at least 15 minutes prior to the nominal PK/ADA/nAb blood collection time point and to allow completion of the ECGs prior to collection of PK/ADA/nAb sample.

Standard 12-lead ECGs will be recorded after the participant has been resting at least 10 minutes using a CAM-14 module. Single ECGs will be collected at the time points noted in the SoA (Section [1.3](#)). Additional ECGs will be performed at the discretion of the Investigator.

Telemetry and ECG readings will be performed in a supine position after the allotted time specified above. During the infusion, procedures will be performed in a semi-supine/semi-reclined position.

The Investigator will be responsible for reviewing the ECG to assess whether the ECG is within the reference limits and to determine clinical significance of the results. If necessary, the Investigator has the right to override the interpretation and intervals as measured by the ECG machine. The ECG will be assessed for the following measures: P wave, QRS complex, U wave, QRS duration, QT interval, QTcF, T wave, ST segment, RR interval, PR interval, and qualitative results.

---

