3 INVESTIGATIONAL PLAN

3.1 Overall Study Design and Plan

This is a single-center, randomized, double-blind, placebo-controlled, first-in-human (FIH), single IV infusion of sequential ascending doses of XTMAB-16 in normal healthy male and female participants.

A total of 24 normal healthy adult participants will be enrolled and assigned into 2 treatment cohorts with 12 participants (9 on XTMAB-16 and 3 on placebo) in each cohort as shown in [Table 1](#). Participants will receive a single IV infusion of 2 or 4 mg/kg of XTMAB-16 or placebo on Day 1.

Figure 3-1 Study Design

Abbreviations: FU = follow-up.

Table 1 Dose Cohorts

Cohort	Dose	Escalation Factor	XTMAB-16	Placebo ^a	Total
1	2 mg/kg	-	9	3	12
2	4 mg/kg	2 x	9	3	12

^a The matching placebo will be identical to the XTMAB-16 in terms of volume and infusion duration.

For all cohorts, a sentinel group of 2 participants (1 assigned to XTMAB-16 and 1 assigned to placebo) will be dosed at least 48 hours before the remaining participants in the same cohort. To maintain the treatment blind, study treatment will be prepared by an unblinded pharmacist according to the treatment assignment who will appropriately label the study drug for administration in a way that maintains the treatment blind to clinical research unit (CRU) staff and the participant.

After blinded review of the available safety and laboratory data of the sentinel group by the Principal Investigator (PI), if no notable safety signals are identified, the remaining participants within the same cohort will be dosed. Participants within a cohort should be dosed at least 1 hour apart. If there are no safety concerns, the participants in Cohort 2 will receive XTMAB-16 after at least 14 to 21 days clinical assessment of the participants at Cohort 1.

After a screening period of up to 28 days, participants will be admitted to the CRU on Day -2 for COVID-19 testing and baseline procedures. After confirmation of eligibility, participants will be randomly assigned to treatment (1:1 XTMAB-16 to placebo for sentinel cohort, 4:1 for remaining participants) and administered study drug on Day 1. Participants will remain at the CRU through Day 8 for PK, biomarkers, anti-drug antibody (ADA), and safety assessments, and will be discharged on Day 8 once all procedures for that day have been completed. Participants will return to the CRU on Days 15, 29, 43, 57, and 71 (End of Study/safety follow-up).

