3.2 Endpoints and Associated Variables

3.2.1 Primary Endpoints

Safety and Tolerability

- The incidence of treatment-emergent adverse events (TEAEs) and serious adverse events (SAEs).
- Observed values and change from Baseline in safety laboratory tests (hematology, clinical chemistry, urinalysis) by visit.
- Observed values and change from Baseline in ECG parameters by visit.
- Time-matched Baseline and 50-hr post dose digital ECG parameters monitoring.
- Observed values and change from Baseline in vital signs.

Immunogenicity

- Number and percentage of participants by cohort who test positive for XTMAB-16 anti-drug antibody (ADA) at Baseline, Day 29, Day 57, and Day 71
- Number and percentage of participants by cohort who test positive for XTMAB-16 neutralizing antibody (nAb) at Baseline, Day 29, Day 57, and Day 71

Biomarkers

Absolute and percent change from Baseline in the following biomarkers:

- Angiotensin converting enzyme (ACE)
- soluble IL-2 receptor (sIL-2R)
- Interleukin 6 (IL-6)
- soluble TNF α (sTNF α)

Other relevant biomarkers may be assessed to better understand PK/PD relationships.

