Descriptive statistics (n, mean, SD, median, lower quartile, upper quartile, minimum, maximum) for absolute values and changes from baseline will be presented by dose cohort and pooled placebo group. A categorical QTc analysis will also be performed.

A summary of the number and percentage of participants with QTcF intervals exceeding some predefined upper limits (e.g. >450ms, >480ms, >500ms for measured values as well as. >30ms, >60ms for changes from baseline) of ECG parameters will be displayed in a frequency table.

Mean QTcF values (\pm SD) over time per dose and pooled placebo will be presented graphically on Safety set.

If findings on telemetry are identified, a further concentration QT analysis (tie-matched QT and QTc analysis for XTMAB-16 and placebo) **may** be further evaluated. ER analysis consists of the following:

1. A linear mixed effects model with Δ QTcF as the dependent variable, drug plasma concentration as a continuous covariate, treatment (active or placebo) as categorical factor, and a random intercept for each participant. Note: concentration values are set to 0 for placebo participants.
2. The predicted mean $\Delta\Delta$ QTcF (placebo corrected, change from baseline) at the observed geometric mean Cmax (i.e., the product with the slope estimate treatment effect [active – placebo]) will be calculated. Two-sided 90% CIs of the estimate will be calculated using a bias-corrected nonparametric bootstrap with 1,000 resamples and participant as the unit of resampling. Note: Bootstrap is used to provide robust estimate for the 90% CI. Resampling will be done independently for the active and the placebo participants. For each resample, the model will be fitted and the predicted mean $\Delta\Delta$ QTcF will be computed at the geometric mean Cmax determined from the resampled data. The 90% CI will be determined from the distribution of resampled predicted values.
3. Decisions to classify the risk QTprolongation induced by XTMAB-16, the upper bound of the two-sided 90% CI for the $\Delta\Delta$ QTcF effect of XTMAB-16 as estimated by ER model should be <10ms at the observed geometric mean Cmax to exclude a risk QT prolongation induced by XTMAB-16. (reference: ICH E14 Guideline: The Clinical Evaluation of QT/QTc Interval Prolongation and Proarrhythmic Potential for Non-Antiarrhythmic Drugs Questions & Answers (R3))

Physical Examination

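### The concentration-QT model has no time term, so a time-varying shift shared by drug and placebo can bias the estimate held against the 10 ms limit

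*SAP*

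**What the plan says.** SAP 4.11.4 (ECG, exposure-response analysis) sets out three steps. Step 1 is a linear mixed model for change in QTcF with "drug plasma concentration as a continuous covariate, treatment (active or placebo) as categorical factor, and a random intercept for each participant", noting that "concentration values are set to 0 for placebo participants". Step 2 predicts the placebo-corrected change at the observed geometric mean Cmax, with a 90% interval from a "bias-corrected nonparametric bootstrap with 1,000 resamples and participant as the unit of resampling". Step 3 gives the decision rule: the upper bound "should be <10ms at the observed geometric mean Cmax to exclude a risk QT prolongation induced by XTMAB-16". Protocol 9.4.2.1 leaves the definition of this analysis to the SAP, so no other text supplies a time or baseline term.

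The analysis is conditional: "If findings on telemetry are identified, a further concentration QT analysis" may be evaluated. The SAP calls it time-matched, and 3.2.1 lists "Time-matched Baseline and 50-hr post dose digital ECG parameters monitoring" as an endpoint. Footnote k of the schedule of assessments places Day -1 telemetry extraction at 1, 2, 3 and 8 hours, with the Day 1 predose reading matched to 24 hours; no match is listed for 50 hours. SAP 4.11.4 also gives a general ECG baseline taken before administration. Step 1 does not say which baseline defines the change, or whether the model uses telemetry times or all visits. Step 2 does not say whether Cmax is per dose or pooled.

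**The concern.** In active participants concentration is largely a function of time since infusion. Suppose QTcF moves over time for reasons unrelated to drug and equally in both arms. The treatment term absorbs the average of that movement. Its pattern over time has nowhere to go except the concentration slope and the residual. Placebo participants could show the pattern, but with concentration fixed at 0 and no time term they contribute nothing to separating it from the slope.

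The design offers a possible source. For telemetry and ECG readings, Protocol 8.2.4 says "During the infusion, procedures will be performed in a semi-supine/semi-reclined position" and supine otherwise, so posture may change near Cmax in both arms. Effects of the infusion itself, or of confinement against later outpatient visits, are other candidates. The slope feeds a rule with a fixed limit, so a few milliseconds either way could exclude a real effect or fail to exclude an absent one. The participant-level bootstrap does not help: it describes the spread of the biased estimate.

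**Working it through.** The documents give no SD, power or sample size for this analysis, so there is no planned figure to reproduce.

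**Inputs from the documents.** "12 participants (9 on XTMAB-16 and 3 on placebo) in each cohort", hence 18 active and 6 placebo. Projected Cmax 47.8 and 95.7 µg/mL (Protocol Table 3). Half-life 203 h, from ln 2 × 14000/47.8 in Table 3, up to 327 h (mouse data, Protocol 4.2). Telemetry times 1, 2, 3, 8, 24 and 50 h; ECG visits to 1682 h.

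**Assumptions.** Residual SD σ = 6 ms; SD of the participant intercept in the change score (baseline error) τ = 6 ms; rise to Cmax over a 2-hour infusion, then mono-exponential decline; shifts of 5 to 10 ms; true drug effect 0.

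**Formula.** The prediction is treatment effect + slope × C. In this balanced layout the treatment estimate is the active-minus-placebo mean less slope × c̄, where c̄ is the mean active concentration. Hence bias(C) = b × (C − c̄), with slope bias b = W_cs/(W_cc + λB_cc) and λ = σ²/(σ² + nτ²). W_cs is the within-participant cross-product of concentration and shift; W_cc and B_cc are the within- and between-participant sums of squares of concentration, all in active participants.

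**Worked case.** Half-life 250 h, telemetry times, shared shift 0, −5, −5, −2, 0, 0 ms.
- Concentration as a fraction of Cmax: 0.500, 1, 0.997, 0.984, 0.941, 0.875; mean 0.883; sum of squared deviations 0.1869; cross-product with the shift −1.359.
- Sum of Cmax: 9 × (47.8 + 95.7) = 1291.5. Sum of Cmax²: 9 × (47.8² + 95.7²) = 102,990.
- W_cs = 1291.5 × (−1.359) = −1755. W_cc = 102,990 × 0.1869 ≈ 19,250.
- λ = 36/(36 + 6 × 36) = 1/7. B_cc = 6 × 18 × (0.883 × 23.95)² ≈ 48,300, so λB_cc ≈ 6,900.
- b = −1755/26,150 = −0.0671 ms per µg/mL. c̄ = 0.883 × 71.75 = 63.3.
- Bias at 95.7: −0.0671 × 32.4 = **−2.2 ms**. Bias at the pooled geometric mean √(47.8 × 95.7) = 67.6: −0.0671 × 4.3 = **−0.3 ms**.

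**Other shifts, half-life 203 to 327 h** (signs reverse with the shift; a shift of half the size gives half the bias):

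| Times | Shift in both arms | Bias at 4 mg/kg Cmax (ms) | Bias at pooled Cmax (ms) |
|---|---|---|---|
| either | constant | 0 | 0 |
| 1–50 h | 0, −5, −5, −2, 0, 0 | −2.0 to −2.4 | −0.2 to −0.4 |
| 1–50 h | −10 at 1 and 2 h | +4.1 to +4.4 | +0.5 to +0.6 |
| 1–50 h | −10 through 8 h | +0.4 to +1.2 | +0.1 |
| all visits | −10 through 8 h | −3.2 to −3.7 | −1.4 to −1.8 |
| all visits | linear rise of 10 by 1682 h | −4.9 to −5.0 | −2.2 to −2.4 |

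Protocol 4.3 refers to a two-compartment model. If 30 to 50% of Cmax is assumed to decline with a 24-hour half-life, the second row becomes −3.5 to −4.1 ms (pooled −0.8 to −1.2).

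**With a categorical time factor** a shared shift is an exact combination of the time columns, so the bias is 0.00 ms in every row.

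**Effect on the rule.** 400 simulated trials per scenario, all visits, bootstrap with 400 resamples, residual SD 7, baseline-error SD 5, between-participant SD 10 ms, Cmax CV about 20%, half-life 250 h. With a true effect of 10 ms at 95.7 µg/mL, the upper bound fell below 10 ms in 31% of trials under a −10 ms shift in the first 8 hours and 18% under −5 ms, against about 7% with no time-varying shift. Adding the time factor brought the 31% to 9%. With a true effect of 0 and a +10 ms shift, correct exclusion was 82% without the time factor and 95% with it.

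**The case against.** **Time matching may already deal with much of this.** If change in QTcF is taken from the Day -1 time-matched readings, repeatable clock-time and meal patterns at 1, 2, 3, 8 and 24 hours are subtracted. Posture may be too: footnote k and Protocol 8.2.4 ask for a semi-reclined rest before telemetry extraction, although both also say supine outside the infusion. This stands in part. Step 1 does not tie its change score to that baseline, nothing is matched at 50 hours or later visits, and infusion-specific effects would remain.

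**The analysis may never be run, and other summaries do not depend on it.** This stands. Descriptive and categorical QTcF summaries are planned regardless, and Protocol 9.1 plans no hypothesis testing.

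**The size depends on chosen shifts.** This stands. No document gives a drift pattern; sign and size change with its shape, the times included and the Cmax used.

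A reader might infer three stronger claims. One is that omitting baseline QTcF also lets common shifts pass for a drug effect. It does not: adding baseline alone left the simulated bias at −3.20 ms (all visits, −10 ms through 8 hours, true effect 0). Another is that any shift common to both arms biases the result; constant ones cancel. The third is that the 10 ms rule would often pass a harmful drug. High false-exclusion rates arise only for particular assumed drifts judged at the 4 mg/kg Cmax.

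**Conclusion.** The point holds as a limited one. Step 1 lacks a time term, and a time-varying shift shared by both arms and correlated with concentration biases the slope and the prediction compared with 10 ms.

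Under the assumptions above, with mono-exponential decline, shifts of 5 to 10 ms around the infusion or first 8 hours give from near 0 to about 4 ms in either direction at the 4 mg/kg Cmax. A slow 10 ms drift across all visits reaches about 5 ms, and a fast distribution phase raises the telemetry-time figures. At the pooled geometric mean Cmax the bias is under 1 ms on telemetry times with mono-exponential decline. If all visits enter it is 1.4 to 1.8 ms for the first-8-hour shift and up to 2.4 ms for the slow drift.

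The mechanism and the zero bias with a time factor do not depend on the assumed values; the magnitudes do. If step 2 means slope × Cmax without the treatment effect, the multiplier becomes C instead of C − c̄, and the worked case gives −0.0671 × 95.7 = −6.4 ms. The documents do not show that such a shift will occur, and the matter is moot if the analysis is not triggered. It is a cheap improvement to a model that is already written down.

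**What to change.** Add nominal time point as a categorical fixed effect to step 1, keeping concentration, treatment and the random intercept, and refit that same model in each bootstrap resample. This removes the bias. Add centred baseline QTcF as a covariate for precision (SE lower by 0 to 9% under the SDs tried) and for protection against chance imbalance with 6 placebo participants, not as a cure for common shifts.

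In the same edit, state whether change in QTcF uses the time-matched Day -1 or the predose baseline, which time points enter, whether Cmax is per dose or pooled, and that the prediction is treatment effect plus slope × Cmax if that is intended.

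The cost is one model statement and no new data. The time factor uses 5 degrees of freedom on telemetry times. When no time effect exists, it raises the SE by about 6 to 7% at the 4 mg/kg Cmax (3.28 to 3.49 ms in the worked case) and by under 1% at the pooled Cmax. If all 14 postdose times enter, it uses 13 degrees of freedom and the SE rises by about 5 to 8% at the 4 mg/kg Cmax, under the two sets of SDs used above (6 and 6 ms; 7 and 5 ms).

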4.12 Other Analyses

4.12.1 Immunogenicity

If ADA or nAb are detected, a direct link model may be used to describe the relationship between the serum concentration of XTMAB-16 and ADA or nAb levels, as AUC and time point concentration measurements to explore the time-dependence.

If ADA or nAb are detected, a summary table of PK parameter by ADA and nAb status (Positive or Negative) will be provided using PK analysis set.

Anti-drug antibodies and nAb at each sampling time will be summarized with descriptive statistics (N, mean, SD, coefficient of variation [CV], geometric mean, geometric CV, median, minimum, and maximum) for each dose cohort and Day.

4.12.2 Biomarker Analysis

Biomarker analysis of ACE, sIL-2R, IL-6, and sTNF α will be based on Biomarker Set.

All participants without any major deviations related to study drug administration and for whom any biomarker (or effect) data are available will be included in the biomarker analysis. However, participants being included in this population and having received only placebo will also be included as part of this data set.

Percent change from Baseline over time and total (absolute) change from Baseline will be analyzed.

4.12.2.1 Biomarker Concentration-Time Data

Biomarkers (ACE, sIL-2R, IL-6, and sTNF α) at each biomarker sampling times will be summarized with descriptive statistics (N, mean, SD, CV%, geometric mean, geometric CV%, median, minimum, and maximum) for treatment, day, and nominal timepoint.

For presentation in biomarker summary tables if less than 4 significant digits, all summary statistics will be tabulated to one more significant digit compared to the source data, otherwise up to a maximum of 4 significant digits, with exception of N, and n that will be presented as whole numbers, CV% and geometric CV% that will be presented to 1 decimal place.

To visualize the comparison between treatment, the following descriptive biomarker graphs will be generated. For each figure participants belonging to each category will be shown on the same plot with separate figures for each level of dose. Figures will be displayed in unique line and marker color, line style and marker for each plot in the graph. For all biomarker-time plots, linear scale will be used for both x-axis and y-axis. The following plots will be generated for each of biomarkers.

- Figure xx.1: Individual Biomarker-Time Profiles (Absolute change and percent change from Baseline) (Biomarker Set)
- Figure xx.2: Mean (\pm SD) Biomarker-Time Profiles (Absolute change and percent change from Baseline) by dose and placebo groups (Biomarker Set)

4.12.2.2 Biomarker Parameters

These biomarker (or effect) parameters will be obtained, if data permit: area under the effect-time curve (AUEC), maximum observed effect ($E_{max,obs}$), and time to reach maximum observed effect ($t_{E_{max,obs}}$). The overall results of the biomarker assessments will determine whether these specific analyses will be performed.

Biomarker parameters will be provided by CPMS group. Biostatistics group will use this data for calculation of biomarker parameter summary statistics tables.

Biomarker parameters will be calculated by non-compartmental analysis methods from the biomarker-time data using Phoenix® WinNonlin® (Version 8.2) or higher following these guidelines:

- Actual sampling times relative to the start of infusion rather than nominal times will be used in the calculation of all derived biomarker parameters.
- There will be no imputation of missing data.

Biomarker parameters will be listed by treatment and subject for the Biomarker Set. Biomarker parameters will be summarized by different dose and placebo groups.

For presentation in biomarker parameter summary tables if less than 4 significant digits, all summary statistics will be tabulated to one more significant digit compared to the source data, otherwise up to a maximum of 4 significant digits, with exception of N, and n that will be presented as whole numbers, CV% and geometric CV% that will be presented to 1 decimal place.

4.13 Determination of Sample Size

The selection of 24 participants (12 per cohort) was based on feasibility and precision around the estimates for target variables associated with the primary and secondary endpoints. No sample size calculation was performed.

4.14 Changes in the Conduct of the Study or Planned Analysis

None.

6 APPENDICES

6.1 Schedule of Assessments

Table 8 Schedule of Assessments

Week	Screening	Baseline	Treatment Period												EOS		
	-4 to -1		1				2	3	4	8	15	29	43	57	71		
Day	-28 to -3	-2 ^a															
Window	-	-	-	-	-	-	-	-	-	-	±24 hrs	±24 hrs	±24 hrs	±24 hrs	±3 days		
PK Hour (from start of infusion)			0	1	2(T)	3	8	14	24	50	74	170	338	674	1010	1346	1682
Informed consent	X																
Inclusion/exclusion	X	X															
Demographics	X																
Medical history	X	X															X
Physical examination ^b	X	X	X								X	X	X	X			X
Height	X																
Weight	X	X															
Serum pregnancy test ^c	X	X															X
Urinalysis	X	X									X	X	X	X	X	X	X
HIV, HBsAg, HCV, COVID-19 ^d , TB	X	COVID-19 Only															
Urine drug abuse screen ^e	X	X															
Participant confinement ^f			X														
Vital signs ^{g,h}	X	X	X	X	X	X	X	X	X	X	X	X	X	X	X	X	X
ECG ^{g,k}	X	X	X	X	X	X	X	X	X	X	X	X	X	X	X	X	X
Telemetry ^k			X														
Biochemistry ^{g,l}	X	X	X						X	X	X	X	X	X	X	X	X
Hematology ^g	X	X	X						X	X	X	X	X	X	X	X	X
PK ^{g,i}		X	X	X	X	X	X	X	X	X	X	X	X	X	X	X	X
Biomarkers ^{g,j}		X			X			X	X	X	X	X	X	X	X	X	X
ADA/nAb ^m		X									X	X	X	X	X	X	X
Infusion of study drug			X														
Concomitant medications	X		X												X	X	X
Adverse events	X		<————→														

Abbreviations: ACE = angiotensin converting enzyme; ADA = anti-drug antibody; ECG = electrocardiogram; EOS = end of study; FU = follow-up; HBsAg = hepatitis B antigen; HCV = hepatitis C virus; HIV = human immunodeficiency virus; IL-6 = interleukin 6; nAb = neutralizing antibodies; PK = pharmacokinetics; sIL-2R = soluble IL-2 receptor; sTNF α = soluble tumor necrosis factor alpha; TB = tuberculosis.

- a Assessments at Day -2 may be performed on Day -1, as needed, by the clinical research unit, but must be performed no later than Day -1.
- b A full physical examination will be performed at Screening, Baseline, Day 8, and Day 71. An abbreviated physical examination will be performed predose on Day 1, and Days 15, 29, and 43. See Section 8.2.1 for a description of the physical examination.
- c For women of childbearing potential only. At Baseline, an FSH test will be run to confirm a postmenopausal state in women under 60 years old and not using hormonal contraception or hormone replacement therapy.
- d At each visit, participants will have a temperature check and will be asked if they have had exposure to someone known to have COVID-19. If the temperature is above 100°F (37.7°C) or the answer is "yes," participants will be tested for COVID-19. Participants who receive a COVID-19 vaccine prior to study entry must receive the final vaccine at least 30 days before dosing and will be tested for COVID-19 as per the SoA. Participants who wish to receive the COVID-19 vaccine after dosing must wait until after Week 4 PK sampling and other assessments have been completed. COVID-19 vaccination and any adverse reaction to the vaccine must be reported.
- e This will include a blood draw to test for blood alcohol levels.
- f From check-in at Day -2 to discharge from the unit on Day 8. Since the participants will be immunocompromised by administration of study treatment, the participants should be instructed to quarantine at home for 6 days after discharge from the clinical research unit.
- g When a meal, vital signs, ECG, or blood sample collection are scheduled at the same time as the study drug administration, the following order will be respected: ECG, vital signs, clinical biomarkers, PK, ADA, safety laboratory samples, and meal. To respect exact timing of PK samples (see Table 8), the other measurements will be done ahead of the scheduled time. The assessment schedule should be adapted to the design of the study.
- h During infusion, blood pressure and heart rate should be collected every 15 minutes for the first hour, every 30 minutes for the second hour, and hourly for 2 hours after the completion of infusion.
- i Blood samples will be collected for XTMAB-16 PK analysis at predose (Hour 0), at 1 hour after the start of infusion, 1 hour after the start of infusion, immediately after the 2-hour infusion (T; infusion termination), and at 3, 8, 14 hours on Day 1, and at 24 hours (Day 2), 50 hours (Day 3), 74 hours (Day 4), 170 hours (Week 2, Day 8), 338 hours (Week 3, Day 15), 674 (Week 4, Day 29), 1010 (Week 6, Day 43), 1346 hours (Week 8, Day 57), and 1682 hours (Week 10, Day 71) postinfusion of XTMAB-16 or placebo. All sampling time points after time T refer to time from the start of infusion. Acceptable windows for PK sample collection are provided in Table 8. The exact time of sample collection must be recorded on the eCRF.
- j Blood samples will be collected to evaluate biomarker concentrations of ACE, sIL-2R, IL-6, and sTNF α .
- k Single 12-Lead ECGs will be collected at all time points. Additional ECGs will be performed at the discretion of the Investigator. Telemetry recording will begin on Day -1 and continue through 50 hours after the start of infusion. At specified time points, for extraction of telemetry data, participants should be in a semi-reclined resting position for at least 10 minutes prior to the target time of data extraction (at least 15 minutes when coinciding with PK/ADA/nAb blood collection). On Day -1, resting periods for telemetry data extraction should occur at 1, 2, 3, and 8 hours (corresponding to the projected time points on Day 1). On Day 1, resting periods for telemetry data extraction should occur at predose (to match the time point for 24 hours after the start of infusion) and 1, 2, 3, 8, and 24 hours after the start of infusion. A resting period for telemetry data extraction will also occur at 50 hours after the end of infusion. During infusion, data will be collected in a semi-supine/semi-reclined position, and for all other readings, data will be collected in a supine position.
- l Tryptase levels will be assessed at Baseline for all participants. For any participant who experiences anaphylaxis within 4 hours after the end of infusion, and additional sample for assessment of tryptase levels should be collected as soon as is reasonable. See Appendix 5 for diagnosis and treatment of anaphylaxis.

- m Blood samples for PK/ADA/nAb will be collected for analysis from participants who experience an SAE that is also considered related to study treatment.

Table 9 Grading of Injection Site Reactions

Local Reaction to Injectable Product	Mild (Grade 1)	Moderate (Grade 2)	Severe (Grade 3)	Potentially Life Threatening (Grade 4)
Pain	Does not Interfere with activity	Repeated use of non-narcotic pain reliver > 24 hours or interferes with activity	Any use of narcotic pain reliever or prevents daily activity	Emergency room (ER) visit or hospitalization
Tenderness	Mild discomfort to touch	Discomfort with movement	Significant discomfort at rest	ER visit or hospitalization
Erythema/Redness*	2.5 - 5 cm	5 – 10 cm	>10 cm	Necrosis or exfoliative dermatitis
Induration/Swelling**	2.5 - 5 cm and does not interfere with activity	5.1 – 10 cm or interferes with activity	>10 cm or prevents daily activity	Necrosis

* In addition to grading the measured local reaction at the greatest single diameter, the measurement should be recorded as a continuous variable.

